Following recruitment and informed consent, all participants will be assigned unique study identification numbers. Women will complete the enrolment study visit and will then be randomized to either the Transitions intervention or control (enhanced standard of care).

Randomization

Randomization will take place at the end of the enrolment study visit. Women will be randomly allocated to either the Transitions intervention or control using a 1:1 randomization scheme. Randomization numbers will be generated prior to the start of the study and will be placed in sequentially numbered opaque envelopes. Randomization envelopes will be stored in a locked cabinet in the study office at UCT and will be accessed by the project manager when a woman is fully consented and has completed the enrolment visit. Women will be informed of their random allocation at the end of the enrolment visit. Ideally, a one-on-one meeting with the CHW (first visit for those in the Transitions intervention, only visit for those in the enhanced standard of care) would occur the same day as enrolment to aid in retention. If this is not possible the CHW will contact the participant using tracing information detailed below to inform them of the date and time of the first or only one-on-one meeting.

Quantitative measures

At each study measurement visit, a trained interviewer will administer questionnaire-based measures using paper and pencil. The trained interviewer will be blinded to participants' allocation. All study measurement visits will be conducted at a space that is separate from routine care. Most measures have been used previously by our group in this setting (see references in Table of measures, below), and have been translated into isiXhosa and back-translated into English following standard procedures. An additional scale⁴⁶ developed to measure the theoretical constructs of Transition Theory has been adapted for use with women living with HIV for this study and will be translated into isiXhosa and back-translated to English prior to use in the trial.

Linkage of routinely collected clinical data

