Our team has extensive experience in utilizing data from routinely collected electronic medical records in this setting, including for ART and PMTCT outcome assessment.^{60,61} Data will be requested from the Western Cape Provincial Data Centre, and we will use participants' provincial folder number (requested as part of tracing information) to facilitate an accurate electronic data request. Permission to review electronic clinical records of participants will be included in informed consent documents. Following standard procedures, we will request approval from the Provincial Department of Health to access electronic medical records. Established procedures are in place to ensure patient confidentiality. The project manager will link these data to participants' unique participant identifiers.

For the primary outcomes obtained from routine medical records (engagement in care and HIV viral suppression), we will use the following definitions:

- Engagement in care will be classified as any evidence of engagement in routine HIV services, including evidence of: HIV visit attendance; ART collection at a pharmacy; laboratory testing of HIV viral load or CD4 cell count
- HIV viral suppression will be classified as a viral load <200 copies/mL

For the primary outcome, we will use a window of up to 3 months around the 6-month postpartum study visit. In cases where there is evidence of multiple HIV viral load results in this window, we will use the result closest to the 6-month postpartum study visit for the primary outcome. For women who are lost to follow-up, we will use the median time of visits attended among those who are retained at study measurement visits to assess engagement in care and HIV viral suppression. As the primary outcome data will come from routine medical records, all women will have outcome data regardless of retention at study measurement visits.

Routinely collected clinical data will be linked with the written permission of (a) the participant (via informed consent), (b) the research oversight body of the Provincial Government of the Western Cape including the Provincial Data Centre, and (c) the HREC. Established procedures are in place to ensure patient confidentiality.

Aim 3 Qualitative Component

In-depth interviews will be conducted with participants randomized to the intervention condition (n=up to 30) after the completion of follow-ups in order to assess participants' experiences of the

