Contamination between groups is a concern and blinding participants to this type of psychosocial intervention is not possible. Contamination would mean that women in the enhanced standard of care control group may be aware of the Transitions interview, or vice-versa, and change their

behaviours related to their own ART use or retention in care. Some of the primary outcomes (retention in ART care and HIV viral suppression) are objective, thus reducing detection bias. Self-reported ART adherence is subjective and thus we acknowledge that this measure may be biased, however, other behavioral interventions (particularly pilot interventions) have utilized self-reported adherence to understand the behavioral antecedent to viral suppression. Insofar as possible, we will mask study personnel involved in the study measurement visits; in particular, the interviewer administering study measures will be blinded to participants' allocation. All study measurement visits will be conducted at a space that is separate from routine care.

8. Participant retention

Study follow-up & retention

Participants will be followed for 8 months (6 months postpartum). Participants in both arms will attend study measurement visits at enrollment, 3 months postpartum, and 6 months postpartum. These visits will be scheduled and conducted separately from any routine care. Retention activities will focus on study measurement visits. At enrolment, the interviewer will collect detailed tracing information, including participants' full names, addresses, all telephone details; the names, addresses and contact details for two individuals who the participant lives with, and one alternate individual who the participant does not live with. Participants will also be asked to provide their provincial folder number used on routine medical records, for linkage with electronic medical records. At the 3-month postpartum follow-up visit, participants will be asked to update their contact information if needed. Throughout the study, tracing information will be kept in locked filing cabinets, separate from other participant information.

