Sample size considerations: pilot study

The overall goal of this pilot study is to determine feasibility and potential efficacy to support future larger, fully-powered tests of the intervention's efficacy. We fully acknowledge the exploratory nature of this pilot. With a sample size of 60, between two groups, 2 follow-up measurements, controlling for self-reported baseline adherence, $p=0.05$, we will have 29% power of finding a small effect (Cohen's $d=0.30$), 65% power of finding a moderate effect ($d=0.50$), and 98% power of finding a large effect ($d=0.80$). This study will be underpowered to find significant small and moderate effects however, we will be able to calculate an effect size and the direction of its impact to support a larger scale test of the intervention.

The facility that is participating in this study, the Gugulethu MOU, sees approximately 4800 pregnant and postpartum women annually, with an antenatal HIV prevalence of 28%. Thus, we do not anticipate difficulty recruiting this sample within the allotted timeframe.

Sample size considerations: In-depth Interviews (Aim 3)

We propose to interview all of the women randomized to the intervention condition ($n=$ up to 30). Based on our follow-up rates for the longitudinal qualitative cohort (HREC 344/2017), we anticipate at least an 80% retention rate at 6 months postpartum, which equates to an anticipated 24 participants completing in-depth interviews. Based on our previous experiences working with this population, we feel that 24 participants will be enough to reach saturation on key themes related to acceptability of the intervention.

Data management

The study includes data from four sources: (1) interviewer-administered questionnaires; (2) routine electronic medical records; (3) dried blood spots; and (4) IDI with participants randomized to the intervention condition. The collection of data will be conducted by (1) a fieldworker; (2) the project manager; (3) lab-based researcher; and (4) a qualitative interviewer, respectively. Procedures for data collection (regardless of source) will be outlined in SOPs. We have a bank of well-developed SOPs that our group has developed for previous studies. All data management will take place at UCT following procedures established by our group for multiple previous studies.

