Quantitative data will be captured into a custom designed Microsoft Access database. The database will be password-protected following standard password safety procedures, and will be maintained in a firewall-protected UCT server with daily backups. The database will be designed and maintained by the project manager. The study coordinator will direct queries and data

quality assurance (QA)/quality control (QC) activities, and supervise data entry, with oversight from the project manager. Data QA will be in the form of robust database structure and platform, and 'front-end' data checks including real-time database queries. QC will be through data checking scripts to identify out-of-range values, logic violations and missing observations. Queries will be resolved based on reference to the completed questionnaires in question; all data queries and responses will be logged, and edits will be implemented through separate program files.

Qualitative data from IDI will be transcribed verbatim and translated into English. Translations will use unique participant identifiers, not participant names. All electronic files will be encrypted and password protected.

Data analysis

Quantitative data will be exported to Stata Version 14.0 (Stata Corporation, College Station, Texas) for analysis. We will analyze all primary and secondary outcomes preliminarily using simple means and standard deviations and point-biserial correlations to estimate effect sizes where appropriate. For outcomes that are indicative of a possible difference by condition, we will utilize more advanced analytic techniques, i.e generalized estimating equations (GEE), as follows:

To compare the impact of intervention condition on self-reported ART adherence, engagement in ART services and HIV viral suppression, we will utilize a series of generalized estimating equations (GEE) using Poisson distributions where appropriate. Outcome analyses will control for baseline self-reported adherence and any baseline differences on demographic variables. Intervention condition, time of assessment, and condition*time interaction will be entered as model effects. We will use GEEs to predict key psychosocial outcomes (adherence self-efficacy) by intervention condition. If there is evidence of an intervention effect we will explore factors that may modify intervention effects, we will compare intervention effects within subgroups of women based on key demographic clinical and psychosocial characteristics.

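### The project manager handles the allocation envelopes and also collects and links the clinic-record outcomes, and the plan does not mask this role or the coding of those outcomes

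*Combined protocol and SAP*

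**What the plan says.** Four places in the protocol describe the project manager's duties.

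- **Section 7, Randomization.** The numbered opaque envelopes "will be accessed by the project manager when a woman is fully consented and has completed the enrolment visit". The woman learns her arm at the end of that same visit.
- **Section 9, Data management.** Four data sources are listed, the second being routine electronic medical records. The text then assigns collectors in order: "The collection of data will be conducted by (1) a fieldworker; (2) the project manager; (3) lab-based researcher; and (4) a qualitative interviewer, respectively". The second source therefore falls to the project manager.
- **Section 7, Linkage of routinely collected clinical data.** "The project manager will link these data to" the study identifiers. These records supply engagement in care and viral suppression, both called primary there and in section 2.
- **Section 9, Data management.** "The database will be designed and maintained by the project manager".

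Section 7 (Contamination and masking) limits masking to personnel at the study measurement visits, as far as possible. The interviewer is the only person named as blinded. The same paragraph concedes that self-reported adherence may be biased, and sets against it that "Some of the primary outcomes (retention in ART care and HIV viral suppression) are objective, thus reducing detection bias".

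**The concern.** The plan offers the record-based outcomes as the less bias-prone counterpart to self-report. An objective source helps, but it does not by itself make ascertainment independent of arm. Someone must still match folder numbers, decide what to do when a match fails, and recognise evidence of engagement across several kinds of record. The person who collects and links these records is the one who handles the allocations, and the plan provides no separation between the two tasks.

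The stake is the credibility of two of the primary outcomes. Section 9 says the pilot will be used to obtain an effect size and its direction for a larger trial. It also reserves the GEE models for outcomes that look as if they differ by condition, with no threshold given. In a trial this small, a few classifications can affect both.

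**Working it through.** The point concerns roles and rules. The plan states no figure to reproduce, so the passages are set side by side, followed by a check of scale.

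**1. Does one role hold both allocation and record data?** Yes for access to the envelopes, collection of the records and linkage: all three name the project manager. That this person opens the envelopes and knows the arm is an inference from having access to them. It is a strong one, because the allocation is disclosed at the end of the same visit and no other role is named.

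**2. Does masking reach this role?** No. The masking text covers measurement-visit staff. Nothing masks record extraction, separates the allocation list from linkage, or says who codes the outcomes.

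**3. Where is there room for discretion?**

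| Step | What the plan fixes | What it leaves open |
|---|---|---|
| Matching records to women | Electronic request to the provincial data centre by folder number | What is done when a folder number does not match |
| Engagement in care (section 7) | Types of record that count: visit, pharmacy collection, laboratory test; window of up to 3 months around the 6-month visit; median visit time for women lost to follow-up | Any evidence suffices; the listed types are given as included, not as exhaustive |
| Retention (section 2) | Attended HIV clinic appointment in the past 3 months | How this is reconciled with the section 7 definition |
| Viral suppression | Below 200 copies/mL; same window; result closest to the 6-month visit | Little, once a result is matched |

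The two retention definitions can disagree. A woman who collected ART from a pharmacy but attended no clinic appointment is engaged under section 7 and not retained under section 2. Section 7 also states that every woman will have outcome data because the source is routine records. If a woman whose record is not found were counted as not engaged, the effort spent searching would decide her outcome.

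**4. Scale.** Inputs: 43 randomised (Protocol Summary); 1:1 allocation (section 7). The split is not given, so 21 and 22 is an assumption. The shift in one arm's proportion when k women are reclassified is k/n.

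- One woman: 1/22 = 4.5 points; 1/21 = 4.8 points.
- Two women: 2/22 = 9.1 points; 2/21 = 9.5 points.
- At the planned 60, or 60/2 = 30 per arm: 1/30 = 3.3 points for one woman.

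These figures hold for any binary outcome in arms of this size. They show how sensitive the result is to single classifications; they do not show how likely a biased classification is.

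**The case against.** The case for leaving the plan as it is has real weight.

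- The records are created by clinics, pharmacies and laboratories outside the trial and arrive through an electronic request. The plan's claim is only that objectivity reduces detection bias; it does not claim blinded extraction. This stands.
- The window, the closest-result rule and the viral load cut-off are already written down. This stands, and it makes the risk for viral suppression small after matching.
- The folder number is requested with the tracing information at enrolment (section 8), and randomisation comes at the end of that visit. The main matching key is therefore obtained before allocation. This stands for obtaining the number, though not for follow-up of a number that later fails to match.
- Section 10 keeps the key linking names to study identifiers free of research data, and nothing suggests a linkage list that carries arm. This helps, but it does not stop a person who handled the envelopes from knowing the allocations.
- A dried-blood-spot viral load is also planned, with a laboratory researcher collecting those data. That offers a partial cross-check on suppression. It does nothing for retention, and sections 2 and 7 name the clinic-record version as primary.
- The trial is an openly exploratory pilot. That limits the consequence without removing the gap.

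A reader might infer that the project manager personally decides who counts as engaged or suppressed. The documents do not support that: they assign collection and linkage, and leave final coding unassigned. A reader might also infer that intervention-arm women would be searched for harder. No such chasing is described, and finding a genuine record corrects missing data unless effort differs by arm. Designing the database is not outcome assessment and adds no weight.

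**Conclusion.** The overlap of roles is in the text, and so is the absence of any masking for it. The project manager very likely knows each woman's arm and also collects and links the data behind two primary outcomes, and the plan does not say that coding is done without knowledge of arm. The resulting risk is modest and unequal. It lies mainly in record matching and in the broad engagement definition, and is small for viral suppression once a result is matched. Nothing in the documents shows that bias occurred, or that the plan's statement about detection bias is false.

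The conclusion rests on two assumptions: that access to the envelopes means knowledge of the allocation, and that the arms are about 21 and 22 women, so that one reclassification is worth 4.5 to 4.8 points. It is a cheap improvement that should be made, not a flaw that undermines the trial.

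**What to change.** Amend section 7, under both the linkage and the masking headings, to state that:

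1. the record request and the linkage to study identifiers use a participant list without study arm;
2. unmatched folder numbers are followed up under one written rule for all women;
3. engagement and viral suppression are derived by a fixed script, written without arm, after the retention definitions in sections 2 and 7 have been reconciled;
4. the derived file is locked before arm is merged.

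A list without arm does not erase what the project manager already knows. Items 2 to 4 are what remove the discretion. If a person rather than a script codes the outcomes, it should be an existing staff member without access to the allocation. The study coordinator qualifies only if kept blind: the plan nowhere describes that role as blinded, and its data-quality work is overseen by the project manager.

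The cost is a small amount of scripting and a file-lock step, with no new staff or participant procedures. If records have already been extracted, the same script can be run on the raw extract without arm.

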2. STUDY AIM & OBJECTIVES

Study aim

The objective of this study is to identify how influential factors change during key moments of transition during pregnancy and postpartum and to construct an intervention that effectively addresses these moments of transition to bolster ART adherence for mothers living with HIV.

Study approach

This study includes two phases:

1. A longitudinal qualitative cohort to identify and characterize factors that influence women's adherence behaviors as well as perceptions and motivations for continued treatment and engagement in care and examine participants' preferences of adherence intervention structure and delivery, in order to shape the design components of the bio-behavioral intervention.
2. Conduct an open pilot and small scale RCT of the intervention to determine feasibility, and preliminary efficacy of the intervention to improve ART adherence among pregnant and postpartum women living with HIV and in-depth interviews with intervention participants to determine acceptability and to identify ways to refine the intervention for future evaluation.

Note that Phase 1 received ethical approval from UCT HREC previously (HREC: 344/2017). This protocol focuses on Phase 2 (Aims 2 & 3).

For Phase 2, the key outcomes are:

Primary Outcomes

1. Feasibility: Feasibility will be assessed through the number of counseling sessions completed.
2. Preliminary efficacy - ART Adherence: Preliminary efficacy will be assessed as the correlation between study arm and self-reported HIV adherence on the 3 item Wilson ART adherence scale (self-report, 3 item scale recoded as 0-100, 100 indicating perfect adherence in the past month) at 6 months postpartum.
3. Preliminary efficacy- Retention in HIV services: Preliminary efficacy will be assessed as the correlation between study arm and retention in HIV services at 6 months postpartum. Retention in HIV services is measured by clinic records. Retention at 6 months postpartum is measured as attended HIV clinic appointment in the past 3 months.
4. Preliminary efficacy-viral suppression: Preliminary efficacy will be assessed as the correlation between study arm and viral suppression at 6 months postpartum. Viral suppression will be measured by clinic records, with viral suppression defined as HIV viral load less than 200 copies/mL.

Secondary Outcomes

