Following established procedures, we will maintain a simple electronic visit schedule database in Microsoft Access for the study team. Based on participant visits logged in the database, a schedule of expected participant study measurement visits is generated that can be used to provide reminders to participants before visits, or identify missed study visits that require tracing. The database will contain only unique participant identification numbers, and reference to the tracing information (kept in a locked study cabinet in the project office) will be made by the study coordinator. Following our previous approach, retention activities will include reminder phone calls to participants prior to study measurement visits. For women who do not attend scheduled study visits, we will attempt to contact the participant via telephone. If unsuccessful, we will contact one of the pre-designated alternate individuals. If telephone attempts fail, fieldworkers will visit the home address of the participant to trace the participant in person. Note that all participant tracing efforts by fieldworkers (via phone or home visit) do not mention the reason for the contact, or anything regarding HIV/AIDS or ART, under any circumstances (even if the participant themselves is traced). All contacts simply request that the participant come to the clinic the next working day for a health-related issue.

Participants will only be traced by study staff if they are found to have missed a study measurement visit. Tracing of participants who default routine care will be managed by public sector health services. However, if a participant is found to have defaulted ART at a study visit, study staff will urgently refer the participant to the service which they last attended.

Participant withdrawal

All participants may refuse or voluntarily withdraw from the study for any reason and at any time. As part of the informed consent process, staff will state specifically that participation in the study is voluntary and that a participant may refuse participation or withdraw from study participation at any time. Participants will be told that withdrawal from the study will have no effect on their access to health facilities providing any services. All study staff will be trained to ensure that participants have a firm understanding of this concept at the time of the informed consent process, and the informed consent forms will include a statement to this effect.

9. Analytic considerations

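### Retention and viral suppression are defined at 6 months postpartum but timed from the 6-month study visit, so if visits run late their window moves with attendance

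*Combined protocol and SAP*

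**What the plan says.** Section 2 (Study Aim & Objectives, primary outcomes) ties both record outcomes to time since birth. For retention: "Retention at 6 months postpartum is measured as attended HIV clinic appointment in the past 3 months". Viral suppression is assessed as the "correlation between study arm and viral suppression at 6 months postpartum".

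Section 7 (Linkage of routinely collected clinical data) gives the operating rule for the same outcomes: "we will use a window of up to 3 months around the 6-month postpartum study visit". If several viral loads fall inside it, "we will use the result closest to the 6-month postpartum study visit for the primary outcome". For women lost to follow-up, "we will use the median time of visits attended among those who are retained at study measurement visits". The same subsection states that record data will exist for every woman whether or not she attends study visits.

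Section 8 (Study follow-up & retention) describes what follows a missed visit: a telephone call, then an alternate contact, and then "If telephone attempts fail, fieldworkers will visit the home address of the participant to trace the participant in person". A woman who is reached is asked to come in on the next working day. No section gives an earliest or latest date for the 6-month visit, and none links the record window to the delivery date.

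**The concern.** A record outcome can be dated from delivery, which is the same clock for everyone. Section 7 dates it from a study visit instead. If that visit is late, the woman's window is late too, and a woman who is never found is placed on a clock taken from other women's attendance. Two women with identical clinic records could then be classified differently.

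Visit timing arises after randomisation, is plausibly related to engagement in care, and may differ by arm, since the intervention arm has four community health worker sessions running into the postpartum period and the control arm has one. Section 7 (Contamination and masking) relies on these two outcomes as the objective ones that limit detection bias. Tying them to attendance gives up part of that advantage, in a pilot meant to supply effect estimates for a larger trial.

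**Working it through.** The plan states no figure that depends on this rule, so there is nothing to reproduce. The check sets the rules side by side and then gives a hypothetical scale.

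**Which visit date is the anchor?** Section 7 does not say attended or scheduled. A scheduled date would exist for every woman, and no substitute would be needed for those lost. The substitute is itself built from attended visits. The attended date is therefore the natural reading, though it is an inference.

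**How the window moves.** Let the visit be *d* months late (*d* is assumed; the documents give no visit dates). The anchor is 6 + *d* months postpartum. Reading the Section 7 window as plus or minus 3 months, it runs from 3 + *d* to 9 + *d*. With the Section 2 look-back of 3 months applied at the same anchor, it runs from 3 + *d* to 6 + *d*.

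| Delay *d* | Plus or minus 3 months | Look-back 3 months |
|---|---|---|
| 0 | 3 to 9 | 3 to 6 |
| 1 | 4 to 10 | 4 to 7 |
| 2 | 5 to 11 | 5 to 8 |
| 3 | 6 to 12 | 6 to 9 |

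With *d* = 2 and the plus-or-minus reading, a viral load at 4 months is outside the window and one at 10.5 months can be taken as the 6-month result. For a woman with the same records who is never traced, and a retained-women median of 6 months, the 4-month result is inside and the 10.5-month result is outside.

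**Hypothetical scale for engagement.** Inputs:
- 49% disengaged by six months postpartum (Introduction).
- Assumptions: constant hazard from delivery with all women engaged at the start, no return to care, and engagement recorded if the woman is still in care when the window opens, 3 months before the anchor. Both windows above open at that point.

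Hazard = −ln(1 − 0.49)/6 = −ln(0.51)/6 = 0.112 per month.

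Share engaged at window opening = exp(−0.112 × (3 + *d*)):
- *d* = 0: 0.714
- *d* = 1: 0.638
- *d* = 2: 0.571
- *d* = 3: 0.510

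If 20% of one arm is two months late and the other arm is punctual, with no treatment effect, the difference is 0.20 × (0.714 − 0.571) = 0.029, about 3 points. If 30% of one arm and 10% of the other are late, the gap in lateness is again 0.20, and the differences are:
- one month late: 0.20 × (0.714 − 0.638) = 0.015
- two months late: 0.029
- three months late: 0.20 × (0.714 − 0.510) = 0.041

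With equal lateness in the two arms, the expected difference is 0.

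**Set against the trial's size.** Three points is 0.029 × 30 = 0.9 of a woman per arm at the planned 60, or 0.029 × 21.5 = 0.6 at the 43 randomised. At 70% engagement, the standard error of the arm difference is √(2 × 0.7 × 0.3/30) = 0.118 with 30 per arm, and √(0.7 × 0.3 × (1/21 + 1/22)) = 0.140 with 43 women.

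**The case against.** The case for leaving the rule alone has several parts.

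- **Lateness is not shown.** Reminder calls precede visits, tracing follows a miss, and the procedures are the same in both arms. No section reports or predicts a visit two months late. This stands: every delay above is assumed.
- **The visit anchor has a purpose.** Self-reported adherence and dried blood spots are collected at that visit, and the planned models include assessment time. Anchoring there lines the outcomes up. This stands as a modest advantage, but it does not require record data to follow attendance.
- **The median rule does little harm.** If most visits are on time, the median is close to 6 months. True, but then a fixed 6-month anchor gives nearly the same result without borrowing other women's dates. The plan also does not say whether the median is overall or by arm, or from what origin it is counted.
- **The scale model omits something the plan describes.** A woman found at a study visit to have defaulted is re-referred to her ART service (Sections 7 and 8). If the window extends past the visit, her return can count as engagement. This stands, and it can push against the modelled fall.

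A reader might infer that late-traced women are in fact scored at a different postpartum age, or that the rule produces a bias of about 3 points against the arm that attends late. The documents support neither. They give no visit dates and no lateness by arm, and the 3 points depend on one-sided lateness and no return to care.

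**Conclusion.** The point holds as a mismatch between the outcome's definition and its timing rule. Section 2 promises a status at 6 months postpartum; Section 7 measures it around a visit whose date is unrestricted and follows attendance. If visits run late, or differently late by arm, the record outcomes do not describe a common postpartum time and the comparison could be biased. This rests on the attended-date reading, which is strong but inferred.

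Size and direction cannot be determined from the documents. The figure of about 3 points is one scenario; zero is expected under equal lateness, and re-referral at the visit could reverse the sign. Any such bias would be small beside a standard error of 12 to 14 points. The reason to change the rule is that a better one is available at little cost.

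The Section 2 look-back and the Section 7 window also differ, and that affects every woman even when all visits are punctual.

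**What to change.** In Section 7, Linkage of routinely collected clinical data:

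1. Anchor engagement in care and viral suppression at delivery date plus 6 months for every woman, whether or not and whenever she attended.
2. Where several viral loads qualify, take the one closest to that date.
3. Delete the median-visit-time rule for women lost to follow-up.
4. State one window for all women and use the same wording in Section 2. Under the fixed anchor, it would run from 3 to 6 months postpartum if the look-back is kept, or from 3 to 9 months if plus or minus 3 months is meant.

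The cost is a few sentences and no added participant contact. Delivery timing is already needed to schedule the postpartum visits, although the plan does not say how the date is obtained, and for women lost early it may have to come from the linked records. The record outcomes will align slightly less exactly with the self-report and dried blood spot date; a visit-anchored version can be kept as a sensitivity analysis.
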